- -What is the care algorithm for these types of NSTs and how do these differ from patients receiving NSTs in clinic?
- -Are the patients and healthcare providers satisfied with the use of the NST device at home compared to receiving an NST in the specified clinic?
- -What is the cost-effectiveness of this approach for the health system and for patients?

Study Population

Age of Participants: Pregnant women ages 18 and older

Sample Size:

At Utah: 60 All Centers: 60

Inclusion Criteria:

Target population: The target population is high-risk pregnant women.

Accessible population: The accessible population is high-risk obstetric patients receiving care throughout the University of Utah Healthcare system and who receive their NSTs at MFDC.

- Singleton gestation
- Estimated gestational age of 32 0/7 -37 6/7 weeks
- Physician order for twice weekly NSTs
- Live within 60 mile radius of the University of Utah University Hospital or a hospital with an obstetric inpatient unit
- Reliable access to and connectivity with wireless Internet
- Reliable for communication and follow-up

Exclusion Criteria:

- Multifetal gestation
- Maternal age less than 18
- Plans to move prior to end of pregnancy
- No or limited access to internet and/or phone

Design

Observational Research Prospective Clinical Research

Study Procedures

Recruitment/Participant Identification Process:

Participants will be recruited by IRB approved research staff. Patients may be referred by their primary obstetrician, but we will not specifically ask providers to recruit patients.

Flyers and brochures will be placed in public areas throughout our recruitment catchment area including: University of Utah medical school, hospital and hospital clinics, campus boards, restrooms, etc.

We will screen patient appointment logs to determine women who may be eligible for this study. The inclusion/exclusion criteria will be reviewed with each patient's chart. Potentially eligible patients will be identified and invited to enroll upon presenting for a scheduled NST in the University of Utah Maternal Fetal Diagnostic Center.

Informed Consent:

Description of location(s) where consent will be obtained:

Consent will be obtained at clinics within the University of Utah covered entity. This may include: Madsen Clinic, Clinic 4 and the Maternal Fetal Diagnostics Center.

Description of the consent process(es), including the timing of consent:

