the result by a telephone call from the mid-level provider and appropriate follow-up arranged according to the NST management algorithm developed for this study. If the patient has trouble with using the device at home, the patient will be able to talk with the mid-level provider via telephone to troubleshoot issues.

The patient will also continue to receive an NST in clinic weekly, allowing each patient to serve as her own control in terms of NST interpretability, frequency of non-reactive NSTs, and satisfaction. Weekly on-site visits will also allow for educational opportunities and trouble-shooting. These NST schedules will be repeated on a weekly basis until delivery or until the provider discontinues the NST order.

Delivery and maternal / neonatal outcome information will be collected from the electronic medical record. Patients will be contacted after delivery to assess overall satisfaction with the NST at home versus in clinic.

Phase II

Upon completion of phase I enrollment (n=30), a second phase of enrollment will begin. Having demonstrated at-home NST interpretability and feasibility of integration into the healthcare system, the next step will be to use the remote NST testing to demonstrate feasible use in rural/remote settings. This will involve enrollment of up to 30 additional subjects. Inclusion/exclusion criteria, enrollment procedures, and study procedures will be identical to phase I recruitment, with the exception of the following:

- 1. Participants may receive NSTs up to twice weekly at home. During regularly scheduled obstetric visits (every 1 to 2 weeks depending on gestational age and circumstances), NSTs will be performed on site which will allow for educational opportunities and trouble-shooting. However, we will remove the requirement for once weekly on-site testing at the University of Utah Hospital.

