A data collection sheet will be developed and utilized in the study. A demographics intake sheet will be used when enrolling patients. Satisfaction questionnaires will be administered to study participants and involved providers. Patient satisfaction questionnaires will be conducted after the second in-home NST, at 2 weeks intervals after the initial survey if the patient is still pregnant, and at 6 weeks postpartum. Provider questionnaires will be conducted at the end of the study after all patients have been enrolled. An additional questionnaire will be administered to providers regarding the accessibility of the NST monitoring segments and interpretability – this will be conducted at the end of the study. Surveys will be built using REDCap. NST documentation within the electronic medical record (EPIC) will be according to the current NST workflow for on-site NSTs; details regarding management of uninterpretable or non-reactive NSTs will be extracted. Obstetric outcomes will be extracted from the patient's electronic medical record (EPIC).

Inclusion/exclusion criteria for which patients were screened out will be collected. Reasons

eligible patients declined study participation will also be collected.

Procedures performed for research purposes only:

Standard of care for this population includes 2 NSTs per week conducted in the out-patien clinic. Participants for this study will have 1 NST completed in clinic and will complete 1 NST at home, per week. Phase II participants may complete both NSTs at home if they n appropriate eligibility criteria. The only difference with home NSTs is that the NST devic patient-applied and the test is conducted at the patient's home. The test itself, and the interpretation, are not different than standard of care testing. Use of the device at home wi not change the patient's standard of care (twice weekly NSTs). The results of the home an clinic testing will be used to inform clinical care in the same way. Inadequate / uninterpretable tracings are a risk for both home and clinic NST monitoring and will requi further assessment per the described algorithms.

Related questionnaires, as described in study procedures section above, are for research purposes only.

Statistical Methods, Data Analysis and Interpretation

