Sample size calculations: As this is a pilot study relying mostly on descriptive statistics, we will initially enroll 10 high-risk patients for proof-of-concept and to troubleshoot problems in system logistics. We will then enroll 20 high-risk patients to assess the refined system.

Data Collection Instrument

A data collection sheet will be developed and utilized in the study. A demographics intake sheet will be used when enrolling patients. Satisfaction questionnaires will be administered to study participants and involved providers. Patient satisfaction questionnaires will be conducted after the second in-home NST, at 2 weeks intervals after the initial survey if the patient is still pregnant, and at 6 weeks postpartum. Provider questionnaires will be conducted at the end of the study after all patients have been enrolled. An additional questionnaire will be administered to

Protocol Summary (ERICA) IRB_00077591
Page 14 of 17 IRB Approval 8/31/2018

providers regarding the accessibility of the NST monitoring segments and interpretability – this will be conducted at the end of the study. Surveys will be built using REDCap. NST documentation within the electronic medical record (EPIC) will be according to the current NST workflow for on-site NSTs; details regarding management of uninterpretable or non-reactive NSTs will be extracted. Obstetric outcomes will be extracted from the patient's electronic medical record (EPIC).

Inclusion/exclusion criteria for which patients were screened out will be collected. Reasons eligible patients declined study participation will also be collected.

Variables

Covariates:

- Pregnancy details
- EGA at enrollment
- Indication for NST testing
- Obstetric history
 - o Gravida
 - o Para
 - Obstetric complication(s)
- Medical comorbidities
- Substance use
 - o Blood pressure at each NST appointment
 - Pregnancy outcomes
 - Delivery data
 - Presentation at delivery
 - o Infant status liveborn versus stillbirth (antepartum versus intrapartum)
 - Gestational age at delivery
 - Reason for delivery
 - Mode of delivery
 - o Indication for mode of delivery if operative
 - Neonatal gender
 - o Birth weight
 - Apgars
 - Highest level of care required for neonate
 - Highest level of care required for patient
 - Maternal days hospitalized after delivery
 - Neonatal days hospitalized after delivery
 - o Adverse outcomes/obstetric complications
 - Reason for declining study
 - Demographics
 - Maternal age
 - Maternal BMI

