 - Maternal height
 - Maternal weight
 - Race

- Ethnicity
- SES indicators
- Residential zip-code
 - Percent of inhabitants at ____% of the federal poverty level
- o Home rental versus ownership
- Marital status
- o Employment status
- o Individual annual income
- o Family annual income
- o Family wealth
- o Family size
- Highest level of education
- Years of education

Outcome:

- Primary outcome
 - Description of feasibility of integration of NST into healthcare system Steps required to integrate in home NST monitoring into the current healthcare system
 - Obtainability of NSTs
 - Schedule-ability of NSTs
 - Interpretability
- Secondary outcome
 - o NST related
 - Percent of satisfactory NSTs obtained
 - Time required by NST staff
 - Time required by patients
 - Number of abnormal NSTs
 - Length of NSTs
 - Frequency of follow-up needed
 - Frequency of appropriate follow-up according to algorithm
 - o Patient satisfaction
 - Provider satisfaction
 - o Frequency and type of complications identified

Analysis

Analytic approach

Data analysis will use mostly descriptive statistics – parametric and nonparametric statistics will be used as indicated (*Chi*-squared or Fisher's exact test will be used for nominal/binary outcomes; Student's t tests, Wilcoxin rank sum, or Mann-Whitney U will be used for continuous and ordinal variables as needed).

Data management

Data for this study will be obtained from medical records, as well as from administered surveys

of patients and providers. Study data will be saved in an online encrypted RedcapTM database. Access will be granted only to investigators participating in the study.

Data analysis

We will analyze descriptive and analytic statistics using StataTM Version 13 (Texas).

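### Phase I home-versus-clinic contrast is within-woman and repeated, but every binary and rank test named assumes independent observations

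*Combined protocol and SAP*

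**What the plan says.** All references are to the combined protocol and SAP.

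- **Design.** Study Design, Phase I describes a single cohort. The weekly clinic NST is kept, "allowing each patient to serve as her own control in terms of NST interpretability, frequency of non-reactive NSTs, and satisfaction". The section on procedures performed for research purposes only sets the allocation: "Participants for this study will have 1 NST completed in clinic and will complete 1 NST at home, per week". Study Design, Phase I adds: "These NST schedules will be repeated on a weekly basis until delivery or until the provider discontinues the NST order". The number of NSTs per woman is therefore not fixed.
- **Satisfaction.** A secondary research question asks whether patients and providers are "satisfied with the use of the NST device at home compared to receiving an NST in the specified clinic". Phase I adds: "Patients will be contacted after delivery to assess overall satisfaction with the NST at home versus in clinic". Under Data Collection Instrument the patient questionnaire is given after the second home NST, then "at 2 weeks intervals after the initial survey if the patient is still pregnant, and at 6 weeks postpartum".
- **Tests.** Analysis, Analytic approach, says the analysis is mostly descriptive. Chi-squared or Fisher's exact serves nominal and binary outcomes. For other outcomes it lists Student's t tests and then: "Wilcoxin rank sum, or Mann-Whitney U will be used for continuous and ordinal variables as needed".
- **Size.** Sample size calculations gives 10 women for proof of concept and then: "We will then enroll 20 high-risk patients to assess the refined system". No alpha, power, effect size or correlation is stated.

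**The concern.** The only home-versus-clinic comparator in Phase I is the woman herself, so the two settings are correlated within her, and each setting contributes several NSTs. A test for two independent groups ignores both features. The plan's latitude to choose as appropriate is a choice among the listed tests, and no binary or rank test on the list is paired or clustered. Nor is there a rule for how several NSTs from one woman enter an analysis.

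At stake is whether a home-versus-clinic p-value means what it says. For scores, the named rank test would throw away the precision that the own-control design was chosen to give. For NST-level proportions, the error rate can be too low or too high, depending on how much the home–clinic gap differs between women.

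**Working it through.** **Plan's own figures.** Phase I is 10 + 20 = 30 women, and 30 + up to 30 gives the stated 60. These agree. There is no power or precision figure to reproduce.

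**Classification of the named tests.**

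| Test | Independent observations assumed? |
|---|---|
| Chi-squared | Yes |
| Fisher's exact | Yes |
| Rank sum / Mann-Whitney U (one test) | Yes |
| Student's t | Not if run as paired; the plan does not say |

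**Assumptions.** The documents give no correlation, variance component, interpretability rate or follow-up length, so all inputs below are assumed. Tests are two-sided at 5%.

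**Continuous or ordinal outcome, one value per woman per setting, 30 women.** With within-woman correlation ρ, the variance of the home-minus-clinic difference is 2σ²(1−ρ), while a two-sample test assumes 2σ². By normal approximation its true type I error is 2[1 − Φ(1.96/√(1−ρ))]:

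- ρ = 0.3: 1.96/0.837 = 2.34, giving 1.9%
- ρ = 0.5: 1.96/0.707 = 2.77, giving 0.6%
- ρ = 0.7: 1.96/0.548 = 3.58, giving 0.03%

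Simulation of the rank tests themselves agrees:

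| ρ | Rank-sum type I error | Signed-rank type I error | Rank-sum power, 0.5 SD shift | Signed-rank power |
|---|---|---|---|---|
| 0.3 | 1.9% | about 5% | 45% | 59% |
| 0.5 | 0.8% | about 5% | 45% | 72% |
| 0.7 | under 0.1% | about 5% | 43% | 92% |

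**Binary NST outcome: why the direction is open.** Take K women with m NSTs per setting. Let their true probabilities have variance τ² in each setting and correlation r between settings. The true variance of the difference in pooled proportions, minus the variance that chi-squared assumes, is (2τ²/K)[(1−r) − 1/m]. Chi-squared is conservative when 1−r is below 1/m and anti-conservative when it is above. At m = 1 it is conservative for any positive r. At m = 4 the break-even is r = 0.75.

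**Binary NST outcome: size.** The simulation assumes 1 to 7 weeks per woman (mean 4, so about 30 × 4 = 120 NSTs per setting, or 20 × 4 = 80 for the 20 women of the refined system). It sets 90% interpretable in both settings and a between-woman SD of 0.5 to 2.5 logits. Gap SD is the SD across women of the home-minus-clinic logit. Ranges are over the between-woman SD.

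| Gap SD | Chi-squared, 30 women | Chi-squared, 20 women |
|---|---|---|
| 0 | 1.8–5.2% | 2.0–4.7% |
| 0.5 | 2.4–5.7% | 2.5–5.5% |
| 1 | 3.9–7.3% | 3.9–7.3% |
| 2 | 9.9–13.5% | 9.6–12.7% |

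A woman-clustered robust test stays at 4.5–5.6% with 30 women and 3.7–5.4% with 20. Fisher's exact is lower than chi-squared: 0.4–4.7% up to gap SD 1 and about 6–9% at 2.

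**Nearer the ceiling (97%).** Chi-squared gives about 2–5% up to gap SD 1 and about 7–8% at 2. Fisher's exact is about 4% or lower. The robust test itself becomes conservative: 1.9–4.8% with 30 women and 0.9–4.1% with 20.

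**Power of the binary remedy.** At 88% against 96% with 30 women, the robust test has 0.54–0.63 and chi-squared 0.64–0.66. Part of the chi-squared advantage at gap SD 1 reflects mild inflation, but it is also ahead at gap SD 0.

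**The case against.** The strongest reply is that little hangs on these tests. The plan is a pilot, mostly descriptive, with a primary outcome worded as a description of feasibility and no alpha, power or decision threshold. No test is tied by name to the home-versus-clinic contrast. The binary error is modest in most scenarios, absent for Fisher's exact up to a gap SD of 1, and the binary remedy gains no power in the case examined. All of this stands, and it is why the weight is minor to moderate. It does not make the listed binary and rank tests suitable for a contrast the protocol itself defines as own-control.

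The rank-sum entry may be a slip for signed rank. If so, the text still needs correcting, and the binary outcomes remain uncovered.

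Several stronger readings are tempting but not supported:

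- *That no paired analysis is possible under the plan.* Student's t could be paired. Even so, a paired t needs a rule for reducing several NSTs to one value per setting.
- *That false positives are inflated.* The direction cannot be fixed from the documents. Inflation to 10–13% needs a gap SD of 2 logits, which they neither support nor exclude.
- *That the cited device success rates of 92.5% and 99.5% settle the interpretability rate.* They measure completion of steps and data collection. They only make the near-ceiling case worth showing.
- *That satisfaction is certainly paired data.* The plan does not say whether women score each setting or give one comparative rating. With one rating there is no pair to test.
- *That Phase II is affected too.* Home and clinic counts may be unequal there, but no Phase II home-versus-clinic comparison is stated.

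**Conclusion.** The point holds for the Phase I home-versus-clinic contrast: the design is paired and repeated, and the named binary and rank tests are for independent observations. This is a mismatch between two parts of the document, not merely missing detail.

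The consequence is limited to p-values for that contrast. Descriptive estimates and comparisons between different women are untouched, and no stated sample size or error rate is overturned. The clearest loss is for scores and durations: if within-woman correlation is 0.3–0.7, the rank-sum test gives up about 14 to 49 percentage points of power for a 0.5 SD shift (59 − 45 and 92 − 43). For binary NST outcomes the error is small unless the gap varies strongly between women, and smaller near the ceiling. The mismatch itself is certain from the text; its size rests wholly on assumed inputs. Minor to moderate, and worth fixing because the repair is cheap.

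**What to change.** In Analysis, Analytic approach, add one paragraph for the Phase I home-versus-clinic contrast:

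- **Continuous and ordinal outcomes:** reduce to one value per woman per setting (for example mean NST length) and use a paired t or Wilcoxon signed-rank test.
- **Satisfaction:** state whether each setting is rated separately and which questionnaire time point is compared. If rated separately, use the paired tests above. If there is one comparative rating, describe it without a two-sample test.
- **Binary NST-level outcomes** (interpretable, non-reactive): compare proportions with clustering on the woman and small-sample robust standard errors, or analyse each woman's pair of proportions. Where events are very few, report counts without a p-value, because the robust test is also unreliable there.
- **Comparisons between different women:** keep the unpaired tests.

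The cost is a paragraph of wording and slightly more analysis work. No new data are needed. No power gain should be expected for binary NST outcomes; the gain there is a p-value that fits the design.
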